**1. Synopsis**

Protocol Title:
 
A phase IIb, clinical trial to study the safety and efficacy of Pembrolizumab (MK-3475) in combination with TS-1+Cisplatin or TS-1+Oxaliplatin as a First Line Chemotherapy in participants with Advanced or Recurrent Gastric Cancer (KEYNOTE-659).
											

Short Title:
 
Phase IIb study of Pembrolizumab in combination with TS-1+Cisplatin or TS-1+Oxaliplatin in GC.
											

Objectives/Hypotheses and Endpoints:
 
In subjects with PD-L1 positive, advanced gastric or GEJ adenocarcinoma, the following objectives will be applied to Cohort 1 and Cohort 2 separately.
 
  
 Objective/Hypothesis	Endpoint	
   
 Primary	
 
  
 
To evaluate ORR per RECIST 1.1 as assessed by blinded independent central review (BICR).
 
 	 
 
ORR is defined as the proportion of participants who have a confirmed complete response (CR) or partial response (PR).
 
 	
 
 Secondary	
 
  
 
To evaluate the Duration of Response (DOR) per RECIST 1.1 and per iRECIST as assessed by BICR.
 
To evaluate ORR per iRECIST by BICR.
 
To evaluate Disease Control Rate (DCR) per RECIST 1.1 and per iRECIST as assessed by BICR.
 
To evaluate PFS per RECIST 1.1 and per iRECIST as assessed by BICR.
 
 	 
 
DOR defined as the time from the earliest date of qualifying response until earliest date of disease progression or death from any cause, whichever comes first.
 
ORR is defined as the proportion of participants who have a confirmed complete response (CR) or partial response (PR).
 
DCR is defined as the proportion of participants who have a stable disease (SD) or better prior to any evidence of progression.
 
PFS is defined as the time from date of enrollment to the first documented progressive disease (PD). Death due to any cause, whichever occurs first.
 
 	
  
		Objective/Hypothesis	Endpoint	Primary		
 
To evaluate ORR per RECIST 1.1 as assessed by blinded independent central review (BICR).
 
	
 
ORR is defined as the proportion of participants who have a confirmed complete response (CR) or partial response (PR).
 
	Secondary		
 
To evaluate the Duration of Response (DOR) per RECIST 1.1 and per iRECIST as assessed by BICR.
 
To evaluate ORR per iRECIST by BICR.
 
To evaluate Disease Control Rate (DCR) per RECIST 1.1 and per iRECIST as assessed by BICR.
 
To evaluate PFS per RECIST 1.1 and per iRECIST as assessed by BICR.
 
	
 
DOR defined as the time from the earliest date of qualifying response until earliest date of disease progression or death from any cause, whichever comes first.
 
ORR is defined as the proportion of participants who have a confirmed complete response (CR) or partial response (PR).
 
DCR is defined as the proportion of participants who have a stable disease (SD) or better prior to any evidence of progression.
 
PFS is defined as the time from date of enrollment to the first documented progressive disease (PD). Death due to any cause, whichever occurs first.
 

Objective/Hypothesis	Endpoint										
Primary											

 
To evaluate ORR per RECIST 1.1 as assessed by blinded independent central review (BICR).
 
	
 
ORR is defined as the proportion of participants who have a confirmed complete response (CR) or partial response (PR).
 
										
Secondary											

 
To evaluate the Duration of Response (DOR) per RECIST 1.1 and per iRECIST as assessed by BICR.
 
To evaluate ORR per iRECIST by BICR.
 
To evaluate Disease Control Rate (DCR) per RECIST 1.1 and per iRECIST as assessed by BICR.
 
To evaluate PFS per RECIST 1.1 and per iRECIST as assessed by BICR.
 
	
 
DOR defined as the time from the earliest date of qualifying response until earliest date of disease progression or death from any cause, whichever comes first.
 
ORR is defined as the proportion of participants who have a confirmed complete response (CR) or partial response (PR).
 
DCR is defined as the proportion of participants who have a stable disease (SD) or better prior to any evidence of progression.
 
PFS is defined as the time from date of enrollment to the first documented progressive disease (PD). Death due to any cause, whichever occurs first.
 
										

 
To evaluate Time To Response (TTR) per RECIST 1.1 and per iRECIST as assessed by BICR.
 
To assess OS.
 
To evaluate safety.
 
	
 
TTR is defined as a time from the date of enrollment day (a starting day) to the first date of confirmed CR or PR
 
OS is defined as the period from the date of enrollment to the date of death due to any cause.
 
Number of participants experiencing AEs and number of participants discontinuing study drug due to AEs.
 

--	--

**Overall Design:**

Study Phase	Phase IIb
Clinical Indication	First-line treatment for gastric cancer in programmed death-ligand 1 (PD-L1) positive (CPS $\geq$ 1%)
Population	Human epidermal growth factor receptor 2 (HER2/neu) negative subjects with advanced gastric or gastroesophageal junction (GEJ) adenocarcinoma.
Study Type	Interventional
Type of Design	Single-arm multiple cohort
Type of Control	No treatment control
Study Blinding	Unblinded Open-label
Estimated Duration of Study	The Sponsor estimates that the study will require approximately 30 months from the time the first participant signs the informed consent until the last participant's last study-related phone call or visit.

**Number of Participants:**

Approximately 90 participants will be enrolled.

**Treatment Groups and Duration:**

Treatment Groups	
Cohort 1: Pembrolizumab 200 mg fixed dose administered every 3 weeks (Q3W) + oxaliplatin 130 mg/m^2 IV infusion Q3W + TS-1 continuous oral administration twice daily (BID) for 14 days followed by a recovery period of 7 days
 
Cohort 2: Pembrolizumab 200 mg fixed dose administered Q3W + cisplatin 60 mg/m^2 IV infusion Q3W + TS-1 continuous oral administration BID for 14 days followed by a recovery period of 7 days

------------------	--

Duration of Participation
	
Each participant will participate in the study from the time the participant signs the informed consent form (ICF) through the final protocol-specified contact. After a screening phase of 28 days, each eligible participant will be assigned to Cohort 1. After the target sample size of Cohort 1 is reached, allocation to Cohort 2 will be started. The study treatment will continue until disease progression is radiographically documented, when clinically appropriate, confirmed by the site per modified Response Evaluation Criteria in Solid Tumors 1.1 for immune-based therapeutics (iRECIST) for participants treated with pembrolizumab, unacceptable adverse event(s) (AEs), intercurrent illness that prevents further administration of treatment, investigator's decision to withdraw the participant, noncompliance with study treatment or procedure requirements or administrative reasons requiring cessation of treatment, or until the participant has received 35 administrations of pembrolizumab (approximately 2 years).
 
After the end of treatment, each participant will be followed for the occurrence of AEs and spontaneously reported pregnancy as described under Section 9.3.
 
Participants who discontinue for reasons other than radiographic disease progression will have post-treatment follow-up imaging for disease status until disease progression is documented radiographically per RECIST 1.1, and confirmed by the site per iRECIST (for participants treated with pembrolizumab), initiating a non-study cancer treatment, withdrawing consent, or becoming lost to follow-up. All participants will be followed by telephone for overall survival until death, withdrawal of consent, or the end of the study.

----------------------------------	--

2. Schedule of Activities (SoA)

Trial Period:	Screening Phase		Treatment Cycles a										End of Treatment	Post-Treatment		
Treatment Cycle	Tumor Tissue collection/submission	Screening	1			2			3	4	5	Cycle 6 and beyond	Last Dose	Safety Follow-up	Follow Up Visits b	Survival Follow-up c
			Day 1	Day 8	Day 15	Day 1	Day 8	Day 15	Day 1	Day 1	Day 1	Day 1	At time of treatment discon	30 days post last dose	Every 6 weeks	Every 12 weeks post last dose
Scheduling Window (Days) d :	-28 to -1	-21 to -1		± 3	± 3	± 3	± 3	± 3	± 3	± 3	± 3	± 3	± 3	± 7	± 7	± 14
Administrative Procedures																
Informed Consent e	X															
Inclusion/Exclusion Criteria		X														
Subject Identification Card		X														
Demographics and Medical History		X														
Prior and Concomitant Medication Review f			X	X	X	X	X	X	X	X	X	X	X	X		
Clinical Procedures/Assessments																
Review Adverse Events g			X	X	X	X	X	X	X	X	X	X	X	X	X	
12-Lead ECG		X														
Full Physical Examination		X											X			
Directed Physical Examination			X	X	X	X	X	X	X	X	X	X				
Vital Signs and Weight h		X	X			X			X	X	X	X	X			
ECOG Performance Status i		X	X			X			X	X	X	X	X			
Post-study Anticancer Therapy Status															X	X
Survival Status																X
Trial Treatment Administration																
Pembrolizumab j (Cohorts 1 and 2)			X			X			X	X	X	X				
Oxaliplatin k (Cohort 1)			X			X			X	X	X	X				
Cisplatin l (Cohort 2)			X			X			X	X	X	X				
TS-1 m (Cohorts 1 and 2)				X			X		X	X	X	X				
Laboratory Procedures/Assessments: Analysis performed by LOCAL Laboratory																
Pregnancy Test – Serum or Urine n		X				X			X	X	X	X		X		
PT/INR and aPTT o		X														
CBC with Differential l		X		X	X	X	X	X	X	X	X	X	X	X		
Chemistry Panel l		X		X	X	X	X	X	X	X	X	X	X	X		
Urinalysis l		X														

Trial Period:	Screening Phase		Treatment Cycles a										End of Treatment	Post-Treatment		
Treatment Cycle	Tumor Tissue collection/submission	Screening	1			2			3	4	5	Cycle 6 and beyond	Last Dose	Safety Follow-up	Follow Up Visits b	Survival Follow-up c
			Day 1	Day 8	Day 15	Day 1	Day 8	Day 15	Day 1	Day 1	Day 1	Day 1	At time of treatment discon	30 days post last dose	Every 6 weeks	Every 12 weeks post last dose
Scheduling Window (Days) d :	-28 to -1	-21 to -1		± 3	± 3	± 3	± 3	± 3	± 3	± 3	± 3	± 3	± 3	± 7	± 7	± 14
T3 (or Free T3), FT4 and TSH 		X				X				X		X		X		
Serum carcinoembryonic antigen (CEA) p		X							X		X	X p				
Serum CA19-9 p		X							X		X	X p				
Efficacy Measurements																
Tumor Imaging d		X	→	→	→	→	→	→	→	→	→	→	→	→	X	
Tumor Tissue Collection																
Archival or Newly Obtained Tissue Collection f	X															

a. Unless otherwise specified, assessments/procedures are to be performed on Day 1 and prior to the first dose of treatment for each cycle unless otherwise specified.

b. In subjects who discontinue study therapy without documented disease progression, every effort should be made to continue monitoring their disease status by radiologic imaging every 6 weeks (± 7 days) until (1) disease progression as assessed by investigator or qualified designee, (2) death, or (3) the end of the study, whichever occurs first.

c. After the start of new anti-cancer treatment or documented disease progression by investigator or qualified designee, the subject should be contacted by telephone every 12 weeks to assess for survival status. Note: Every effort should be made to ensure telephone contact at least 90 days post discontinuation to capture SAEs/ECIs. The Sponsor may request survival status be assessed at additional time points during the course of the study. All subjects who are not known to have died prior to the request for these additional survival status time points will be contacted at that time.

d. Unless otherwise specified, the window for each visit is ± 3 days. Cycle 1 treatment must be given within 8 days after enrollment.

e. Written consent must be obtained prior to performing any protocol specified procedure. Results of a test performed prior to the subject signing consent as part of routine clinical management are acceptable in lieu of a screening test if performed within the specified time frame (e.g., within 21 days prior to the first dose of trial treatment). Screening number will be assigned when the study informed consent is signed.

f. Concomitant medications – Enter new medications started during the treatment until the Safety Follow-up visit. Record all medications taken for SAEs as defined in Section 9.3.

g. Record all AEs occurring within 30 days after the last dose of trial treatment. Report all SAEs (related and unrelated to trial treatment) and ECIs occurring up until 90 days after the last dose of trial treatment or 30 days after the end of treatment if the subject initiates new anticancer therapy, whichever occurs first. Afterwards, report only SAEs and ECIs that are related to trial treatment.

h. Vital signs to include temperature, pulse, respiratory rate, weight and blood pressure. Height will be measured in screening phase only.

i. ECOG PS for screening is to be performed within 3 days of enrollment. Laboratory tests for screening are to be performed within 7 days of enrollment. See Section 7.1.3 for details regarding laboratory tests. After Cycle 1, lab samples can be collected up to 72 hours prior to the scheduled time point. CBC with Differential and Chemistry panel are to be performed prior to the administration of all the cycles. Thyroid function tests should be collected every 6 weeks (every 2 cycles, e.g., Cycles 8, 10, 12, etc). Unresolved abnormal labs that are drug related AEs should be followed until resolution. Labs do not need to be repeated after the end of treatment if labs are within normal range.

j. Pembrolizumab should be administered on Day 1 of each 3 week cycle after all procedures/assessments have been completed. Pembrolizumab 200 mg should be

Trial Period:	Screening Phase		Treatment Cycles a										End of Treatment	Post-Treatment		
Treatment Cycle	Tumor Tissue collection/submission	Screening	1			2			3	4	5	Cycle 6 and beyond	Last Dose	Safety Follow-up	Follow Up Visits b	Survival Follow-up c
			Day 1	Day 8	Day 15	Day 1	Day 8	Day 15	Day 1	Day 1	Day 1	Day 1	At time of treatment discon	30 days post last dose	Every 6 weeks	Every 12 weeks post last dose
Scheduling Window (Days) d :	-28 to -1	-21 to -1		± 3	± 3	± 3	± 3	± 3	± 3	± 3	± 3	± 3	± 3	± 7	± 7	± 14

administered as a 30 minute IV infusion Q3W. Sites should make every effort to target infusion timing to be as close to 30 minutes as possible. However, given the variability of infusion pumps from site to site, a window of -5 minutes and +10 minutes is permitted (i.e., infusion time is 30 minutes: -5 min/+10 min). The order of administration of pembrolizumab, oxaliplatin/cisplatin and TS-1, pembrolizumab infusion is administered first followed by the oxaliplatin/cisplatin infusion and then TS-1.
 
k. Oxaliplatin 130 mg/m^2 will be administered as a 120 minute IV infusion Q3W on Day 1 of each treatment cycle.
 
l. Cisplatin 60 mg/m^2 will be administered as a 120 minute IV infusion Q3W on Day 1 of each treatment cycle.
 
m. TS-1 40 to 60 mg/body/dose will be orally administered bid at Days 1 to 14 Q3W.
 
n. For women of reproductive potential, a serum pregnancy test should be performed within 72 hours prior to each cycle of trial treatment and 30 days post treatment. A urine test can be considered if serum is not appropriate. Pregnancy tests (serum and/or urine tests) should be repeated if required by local guidelines.
 
o. Coagulation factors (PT/INR and aPTT) should be tested as part of the screening procedures for all subjects. And to be performed within 7 days of enrollment.
 
p. Serum CEA and CA 19-9 should be collected at screening (baseline), Cycle 3 and every 6 weeks (conducted at corresponding study visit; Cycle 5, Cycle 7, etc.) until study treatment discontinuation. When overall response is graded as CR, the examination will be performed 4 weeks after the CR assessment (accepted if performed up to 7 days after a reference day).
 
q. Baseline tumor imaging will be performed within 21 days prior to enrollment. Scans performed as part of routine clinical management are acceptable for use as the baseline scan if they are of diagnostic quality and performed within the allotted screening window for each cohort. The exact same image acquisition and processing parameters are recommended throughout the study. The first on-study imaging time point will be performed 6 weeks (± 7 days) after the subject has been enrolled, or earlier if clinically indicated and will continue to be performed every 6 weeks (± 7 days). When overall response is graded as CR or PR based on RECIST 1.1, the examination interval is changed and imaging that will confirm the best overall response (in case of CR, tumor maker levels will also be measured) will be performed 4 weeks after the last assessment (accepted if performed up to 7 days after a reference day). When assessment consecutively results in CR or PR, confirming the best overall response, examinations will be performed thereafter at an interval of 6 weeks from the day of enrollment. First examination after confirming the best over response as CR or PR will not be required. Imaging should be repeated until PD. Imaging timing should follow calendar days. On-study scans (scheduled and unscheduled) should be submitted to the BICR.
 
r. Tumor tissue from newly obtained core or excisional biopsy (FNA not adequate) and archival tissue sample (where available) should be tested for PD-L1 (evaluation of eligibility). Only PD-L1 positive subjects will be eligible for this trial. Tumor submission can occur up to 28 days prior to enrollment. Consent must be obtained prior to tumor tissue submission/collection. Detailed instructions for tissue collection, process and shipment are provided in the Procedures Manual.
																

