Adverse events (AE) will be monitored throughout the trial and graded in severity according to the guidelines outlined in the NCI Common Terminology Criteria for Adverse Events (CTCAE) version 4.0.

Treatment will continue until documented clinical PD, unacceptable AE(s), intercurrent illness that prevents further administration of treatment, investigator's decision to withdraw the subject, subject withdraws consent, subject's request to discontinue, pregnancy of the subject, noncompliance with trial treatment or procedure requirements, 35 administrations of pembrolizumab (approximately 2 years), or administrative reasons.

Subjects who have evidence of PD by imaging but are clinically stable may continue to be treated at the discretion of the investigator. In addition, subjects who attain an investigator-determined confirmed complete response (CR) may stop the trial treatment after receiving at least 8 administrations of pembrolizumab and at least two additional treatments of pembrolizumab between the confirmation of CR and the treatment discontinuation.

After the end of treatment, each subject will have a 30 day follow-up assessment for AE monitoring (serious adverse events and events of clinical interest (ECI) will be collected for 90 days after the end of treatment or 30 days after the end of treatment if the subject initiates new anticancer therapy, whichever is earlier). Subjects who discontinue treatment for reasons other than PD will have post-treatment follow-up for disease status until PD, withdrawing consent, or becoming lost to follow-up. All subjects will be followed for OS by telephone and other systems every 12 weeks ( $\pm 7$  days) or more frequently based on the necessity until death, withdrawal of consent or the end of the trial, whichever comes first.

[figure not shown]
This study will be conducted in conformance with Good Clinical Practices.

Specific procedures to be performed during the study, as well as their prescribed times and associated visit windows, are outlined in the Study SoA - Section 2. Details of each procedure are provided in Section 9 – Study Assessments and Procedures.

No safety and/or efficacy interim analysis is planned. Statistical analyses will be carried out at the key evaluation time point for each cohort and the end of the study. More details are in Section 10.7.

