### 7.2.3 Dose modification and toxicity management for immune-related AEs associated with pembrolizumab

AEs associated with pembrolizumab exposure may represent an immunologic etiology. These immune-related AEs (irAEs) may occur shortly after the first dose or several months after the last dose of pembrolizumab treatment and may affect more than one body system simultaneously. Therefore, early recognition and initiation of treatment is critical to reduce complications. Based on existing clinical study data, most irAEs were reversible and could be managed with interruptions of pembrolizumab, administration of corticosteroids and/or other supportive care. For suspected irAEs, ensure adequate evaluation to confirm etiology or exclude other causes. Additional procedures or tests such as bronchoscopy, endoscopy, skin biopsy may be included as part of the evaluation. Based on the severity of irAEs, withhold or permanently discontinue pembrolizumab and administer corticosteroids. Dose modification and toxicity management guidelines for irAEs associated with pembrolizumab are provided in [Table 5](#).

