### **9.3.1 Time Period and Frequency for Collecting AE, SAE and Other Reportable Safety Event Information**

All AEs, SAEs, and other reportable safety events that occur after the consent form is signed but before treatment allocation/randomization must be reported by the investigator if the participant is receiving placebo run-in or other run-in treatment, if the event causes the participant to be excluded from the study, or is the result of a protocol-specified intervention, including but not limited to washout or discontinuation of usual therapy, diet, or a procedure.

- All AEs from the time of treatment allocation/randomization through 30 days following cessation of study treatment must be reported by the investigator.
- All AEs meeting serious criteria, from the time of treatment allocation/randomization through 90 days following cessation of study treatment, or 30 days following cessation of study treatment if the participant initiates new anticancer therapy, whichever is earlier must be reported by the investigator.
- All pregnancies and exposure during breastfeeding, from the time of treatment allocation/randomization through 120 days following cessation of study treatment, or 30 days following cessation of study treatment if the participant initiates new anticancer therapy must be reported by the investigator.
- Additionally, any SAE brought to the attention of an investigator at any time outside of the time period specified above must be reported immediately to the Sponsor if the event is considered to be drug-related.

Investigators are not obligated to actively seek AE or SAE or other reportable safety events in former study participants. However, if the investigator learns of any SAE, including a death, at any time after a participant has been discharged from the study, and he/she considers the event to be reasonably related to the study treatment or study participation, the investigator must promptly notify the sponsor.

All initial and follow-up AEs, SAEs and other reportable safety events will be recorded and reported to the sponsor or designee within the timeframes as indicated in [Table 12](#).

Table 12 Reporting Time Periods and Timeframes for Adverse Events and Other Reportable Safety Events

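### The SAE window drops from 90 to 30 days once new anticancer therapy is started, whenever that is, so unrelated SAEs that precede the new therapy can go unreported

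*Combined protocol and SAP*

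**What the plan says.** Section 2 (Schedule of Activities), footnote g, sets the default: "Report all SAEs (related and unrelated to trial treatment) and ECIs occurring up until 90 days after the last dose of trial treatment". It then gives the alternative end: "30 days after the end of treatment if the subject initiates new anticancer therapy, whichever occurs first". Once the window has closed it adds: "Afterwards, report only SAEs and ECIs that are related to trial treatment".

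Section 5.1 has the same rule for SAEs and ECIs, "90 days after the end of treatment or 30 days after the end of treatment if the subject initiates new anticancer therapy, whichever is earlier", and Section 5.1.1.2 repeats it. Section 9.3.1 applies it to SAEs: "or 30 days following cessation of study treatment if the participant initiates new anticancer therapy, whichever is earlier must be reported by the investigator". That section also keeps any SAE outside the period reportable if related; it "must be reported immediately to the Sponsor if the event is considered to be drug-related".

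Four other places bear on the same window:
- Footnote c of the Schedule covers subjects who have progressed or started new therapy. It asks for a telephone contact 90 days or more after discontinuation in order to pick up SAEs and ECIs.
- Section 9.10.3.1 has SAEs and ECIs followed and recorded if they fall within 30 days of the end of treatment or precede new therapy. It does not mention 90 days.
- Table 12 requires no ECI reports after the follow-up period and requires SAE reports within 24 hours of the site learning of the event.
- The pregnancy bullet in Section 9.3.1 gives 120 days, or 30 days with new therapy, but does not say which of the two governs.

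**The concern.** A safety window should be known on the day the event occurs. Here its length depends on something that may happen later. On day 45 nobody can say whether a subject's window is 30 or 90 days, because that depends on whether second-line treatment will follow.

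The usual reason to shorten such a window is that events on a new drug are hard to attribute. This clause can also remove time before any new drug is given. Subjects who go on to second-line treatment are the ones affected. Safety is a secondary objective, Section 10.4.2 lists SAEs and fatal AEs among the parameters reviewed, and Section 5.4.2 says the oxaliplatin combination has no earlier safety data. Section 7.2.3 says immune-related events "may occur shortly after the first dose or several months after the last dose of pembrolizumab treatment". In an open-label study without a control arm, collecting all SAEs regardless of attribution protects against wrong causality calls.

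**Working it through.** The plan gives no figure for this point, so there is none to reproduce. The check is the rule itself, followed by a comparison of passages.

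**1. Literal reading.** Inputs: limits of 90 and 30 days (footnote g); new therapy starts on day *t*; day 0 is both last dose and end of treatment (an assumption, see step 4). For any subject who starts new therapy, window end = min(90, 30) = day 30, whatever *t* is. Days lost before the new drug = *t* − 31 for *t* from 31 to 90, and 60 (days 31 to 90) for a later start.

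| New therapy starts | Window ends (literal) | Days lost before new drug |
|---|---|---|
| day 31 | day 30 | 0 |
| day 60 | day 30 | 29 |
| day 85 | day 30 | 54 |
| day 90 | day 30 | 59 |
| after day 90 | day 30 | 60 |

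**2. Prospective reading.** While no new therapy has started, the condition is unmet and the 90-day limit governs. An SAE on day 45 that the site hears of on day 46 is due within 24 hours (Table 12). Nothing tells the site to withdraw it if new therapy starts on day 85. Days lost: none, provided the site learns of the event before the new therapy starts.

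**3. Where the readings diverge in practice.** After confirmed progression or new therapy, Section 9.10.3.3 and the Schedule move subjects to calls every 12 weeks ± 14 days. The Schedule counts from last dose, so the first call falls at 84 ± 14, that is days 70 to 98. Section 5.1 gives ± 7 days, that is days 77 to 91. The Schedule marks adverse event review at the six-weekly follow-up visits but not under survival follow-up. Suppose a progressed subject has an unrelated SAE on day 45, starts new therapy on day 60 and is called on day 84:
- literal reading: the window closed on day 30, so the SAE is not reportable;
- prospective, judged when the site learns of it: new therapy has started, so it is not reportable;
- prospective, judged when the event occurred: it is reportable.

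The text does not choose among these.

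**4. Reference date.** Footnote g counts 90 days from last dose but 30 days from end of treatment. If end of treatment falls *D* days after last dose, the cut comes at day min(90, 30 + *D*) after last dose. The documents do not give *D*. By assumption: *D* = 0 gives day 30, *D* = 21 gives day 51, and *D* of 60 or more gives no cut.

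**5. Conflicts.**
- For subjects on new therapy, footnote c seeks SAEs and ECIs at 90 days or later, when footnote g has already closed the all-causality window.
- Section 9.10.3.1 ties its alternative cutoff to the start of new therapy; footnote g does not.
- After the window, footnote g still wants related ECIs; Table 12 wants none.

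**The case against.** The strongest reply is that the literal reading cannot be operated. A site cannot know on day 45 what will happen on day 85. With 24-hour reporting the SAE would normally already be in the database, and footnote c and Section 9.10.3.1 both lean towards capture. This stands for events learned of promptly. It does not cover events first heard of at a 12-weekly call, because the 24 hours run from learning of the event.

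Second, immune-related events judged related remain reportable under footnote g, and related SAEs do so at any time under Section 9.3.1. This stands too: the late-onset argument reaches only events wrongly judged unrelated.

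Third, little else is exposed. ECIs in Section 9.3.7 are overdose without symptoms and one liver-test pattern, and the Schedule's last chemistry panel is at the 30-day visit. The stated safety endpoint counts participants with AEs and participants discontinuing study drug for AEs. Off-treatment SAEs after day 30 cannot change the second count, and change the first only for a subject with no earlier AE. This limits the point to SAE and fatal-event summaries.

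**Conclusion.** The clause is defective because it lacks a time condition and four places share the defect. The loss is mainly SAEs judged unrelated, occurring after day 30 and before new therapy, and first learned of after that therapy starts. ORR and the sample size are untouched. Up to 59 days per subject for starts by day 90 (60 for later starts) is the literal-reading maximum, with end of treatment equal to last dose.

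Two stronger conclusions might be inferred, and the documents support neither. One is that the plan simply discards every SAE after day 30 in anyone who later starts new therapy. That takes one of several readings as the only one and passes over the continued reporting of related SAEs. The other is a share of follow-up lost. If 30% to 70% of 40 subjects per cohort started uniformly over days 31 to 90 (mean loss 29.5 days) and the rest not before day 90, the literal loss would be 12 × 29.5 = 354 of 354 + 28 × 60 = 2,034 patient-days (17%), up to 28 × 29.5 = 826 of 826 + 12 × 60 = 1,546 (53%). The documents give neither the proportion nor the timing. The sum counts starts after day 90 as no loss, although the literal reading removes 60 days from them. No SAE rate is given either, so days cannot be turned into events. The number lost cannot be estimated.

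**What to change.** In footnote g and Sections 5.1, 5.1.1.2 and 9.3.1, replace the clause with one rule. All SAEs (and ECIs where the passage covers them) are reported through 90 days after a single named reference date, or until new anticancer therapy starts if that is earlier, but for no less than 30 days. The date the event occurs decides, not the date the site learns of it. With *t* the day new therapy starts, the window ends at max(30, min(90, *t*)). With the reference date held fixed, this is never shorter than now.

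Align footnote c, Section 9.10.3.1 and the ECI rows of Table 12 with that rule, including whether related ECIs are reported after the window. State which limit governs in the 120/30-day pregnancy bullet of Section 9.3.1.

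The cost is one sentence in four places, a consistency edit in the others, and a few more SAE reports from subjects who start new therapy after day 30.
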